6.1.2 Criteria to Escalate from 1000mg to 1500mg

1. Participants must not have any gastrointestinal toxicity > Grade 1 on day of anticipated escalation
 - If toxicity is Grade 2, hold for one week, and re-evaluate
 - If in one week, the toxicity has not resolved to Grade 1 or better, hold treatment for a second week and re-evaluate
 - If after the second week the toxicity has not resolved to Grade 1 or better, consider holding for one additional week
 - If the participant is unable to dose escalate after 3 weeks beyond the expected escalation date maintain at 1000mg or reduce to 500mg for the duration of the study or discontinue treatment at PI discretion
 - If toxicity is Grade 3, hold for 1 week, and re-evaluate
 - If in one week toxicity has not resolved to Grade 1 or better, consider holding for one additional week, and re-evaluate
 - If the participant is unable to dose escalate after 3 weeks beyond the expected escalation date, or without resolution of symptoms to Grade 1 or better, discontinue treatment at PI discretion.

6.2 Criteria to Dose Escalate - Other Toxicities

For all other toxicities thought to be possibly, probably or definitely related to the study medication, the following guidance for dose escalation is advised:

6.2.1 Criteria to Escalate from 500mg to 1000mg

1. Participants must not have any toxicity > Grade 1 on day of anticipated escalation
 - If toxicity is Grade 2, hold for one week, and re-evaluate
 - If in one week, the toxicity has not resolved to Grade 1 or better, hold treatment for a second week and re-evaluate
 - If the participant is unable to dose escalate after 3 weeks beyond the expected escalation date, consider treatment at 500mg for the duration of the study or discontinuation at PI discretion
 - If toxicity is Grade 3, hold medication for 1 week, and re-evaluate
 - If in one week, toxicity has not resolved to Grade 1 or better, consider holding for one additional week, and re-evaluate
 - If the participant is unable to dose escalate after 3 weeks beyond the original expected escalation date, or without resolution of symptoms to Grade 1, maintain 500mg as final dose for the duration of the study, or discontinue altogether at the investigator's discretion

6.2.2 Criteria to Escalate from 1000mg to 1500mg

1. Participants must not have any toxicity > Grade 1 on day of anticipated escalation
 - If toxicity is Grade 2, hold for one week, and re-evaluate
 - If in one week, the toxicity has not resolved to Grade 1 or better, hold treatment for a second week and re-evaluate
 - If after the second week the toxicity has not resolved to Grade 1 or better, consider holding for one additional week
 - If the participant is unable to dose escalate after 3 weeks beyond the expected escalation date maintain at 1000mg or reduce to 500mg for the duration of the study or discontinue treatment at PI discretion
 - If toxicity is Grade 3, hold for 1 week, and re-evaluate
 - If in one week toxicity has not resolved to Grade 1 or better, consider holding for one additional week, and re-evaluate
 - If the participant is unable to dose escalate after 3 weeks beyond the expected escalation date, or without resolution of symptoms to Grade 1 or better, discontinue treatment at PI discretion.

6.3 Dose Modification Schedule

Dose Level	Dose
0 (Starting Dose)	1500mg Daily
-1	1000mg Daily
-2	500mg Daily
-3	Discontinue

Dose Level	Dose
------------	------

0 (Starting Dose)	1000mg Daily
-1	500mg Daily
-2	Discontinue

Dose Level	Dose
0 (Starting Dose)	500mg Daily
-1	Discontinue

- With the investigator's discretion, dose re-escalation can be considered, or an alternative dose ramp up plan or dose management plan proposed
- If a participant needs to be dose reduced during the dose ramp up period, the principal investigator may decide to not escalate further, or escalate after improvement of symptoms

6.4 Toxicity Management Guidelines For Toxicity After Escalation Period

The following guidelines should be followed if thought to be related to the study medication:

Nausea, Vomiting, Diarrhea	Management/Next Dose for Study Drug
≤ Grade 1	No change in dose. Patient should be encouraged to remain on full dose; if unwilling to remain on therapy, stop study treatment for one week. Resume at same dose. If symptoms recur, then reduce to one tablet daily (if applicable) permanently for remainder of study.
Grade 2	Hold until ≤ Grade 1. Resume at one dose level lower, if indicated at PI discretion.
Grade 3	Hold* until ≤ Grade 1. Resume at 1-2 dose levels lower, if indicated at PI discretion.
Grade 4	Off protocol therapy
Recommended management: antiemetics or Loperamide antidiarrheal therapy as needed	

Other Toxicity*	Management/Next Dose for Study Drug
≤ Grade 1	No change in dose. Patient should be encouraged to remain on full dose; if unwilling to remain on therapy, stop study treatment for one week. Resume at same dose. If symptoms recur, then reduce to one dose level

	lower permanently for remainder of study.
Grade 2	Hold until \leq Grade 1. Resume at one dose level lower, if indicated at PI discretion.
Grade 3	Hold until \leq Grade 1. Resume at 1-2 dose levels lower, if indicated at PI discretion.
Grade 4	Off protocol therapy

* all other toxicities include any other hematologic or non-hematologic toxicity that is not listed specifically above.

7. ADVERSE EVENTS: LIST AND REPORTING REQUIREMENTS

Adverse event (AE) monitoring and reporting is a routine part of every clinical trial. The following list of reported and/or potential AEs (Section 7.1) and the characteristics of an observed AE (Section 7.2) will determine whether the event requires expedited reporting **in addition** to routine reporting.

7.1 Expected Toxicities

7.1.1 Adverse Events List for Metformin

Lactic acidosis is an uncommon but serious adverse event associated with metformin administration. The reported incidence of lactic acidosis in patients receiving metformin hydrochloride is very low (approximately 0.03 cases / 1000 patient/years with approximately 0.015 fatal cases / 1000 patient/years).

Other side effects include: Diarrhea, Nausea, Vomiting, Flatulence, Lack of energy/weakness (asthenia), Abdominal pain, Constipation, Distention of the stomach/abdomen, Dyspepsia (heartburn), Dizziness, Headache, Upper respiratory infection, Change or disturbance of taste, Abnormal stools, Low blood sugar (hypoglycemia), Muscle aches (myalgias), Lightheadedness, Dyspnea (shortness of breath), Nail changes, Rash, Increased sweating, Chest discomfort, Chills, Flu-like syndrome, Flushing, and Heart palpitations

7.2 Adverse Event Characteristics

- **CTCAE term (AE description) and grade:** The descriptions and grading scales found in the revised NCI Common Terminology Criteria for Adverse Events (CTCAE) version 5.0 will be utilized for AE reporting. All appropriate treatment areas should have access to a copy of the CTCAE version 5.0. A copy of the CTCAE version 5.0 can be downloaded from the CTEP web site http://ctep.cancer.gov/protocolDevelopment/electronic_applications/ctc.htm.
- **For expedited reporting purposes only:**

- AEs for the agent(s) that are listed above should be reported only if the adverse event varies in nature, intensity or frequency from the expected toxicity information which is provided.
- Other AEs for the protocol that do not require expedited reporting are outlined in the next section (Expedited Adverse Event Reporting) under the sub-heading of Protocol-Specific Expedited Adverse Event Reporting Exclusions.

- **Attribution** of the AE:
 - Definite – The AE is *clearly related* to the study treatment.
 - Probable – The AE is *likely related* to the study treatment.
 - Possible – The AE *may be related* to the study treatment.
 - Unlikely – The AE is *doubtfully related* to the study treatment.
 - Unrelated – The AE is *clearly NOT related* to the study treatment.

7.3 Adverse Event Reporting

- 7.3.1 In the event of an unanticipated problem or life-threatening complications treating investigators must immediately notify the PI.
- 7.3.2 Investigators **must** report to the PI any adverse event (AE) that occurs after the initial dose of study treatment, during treatment, or within 30 days of the last dose of treatment on the local institutional SAE form.
- 7.3.3 Adverse Event Reporting Guidelines

All participating sites will report AEs to the Sponsor-Investigator per DF/HCC requirements, and the IRB of record for each site as applicable per IRB policies. The table below indicates which events must be reported to the DF/HCC Sponsor-Investigator.

- **CTCAE Grade 2 and Grade 3 Events** – that are Unexpected and there is a Reasonable Possibility that the Adverse Event is related to the study intervention.
- **CTCAE Grade 4 Events** – Report all events that are Unexpected. Events that are Expected and listed within the protocol and/or current consent form do not need to be reported to the DFCI IRB. Please note, an event that presents at a higher severity than what is currently listed within the protocol and/or current consent as expected would be considered unexpected and reportable. See protocol for additional reporting requirements (to sponsor, FDA, etc.).
- **ALL CTCAE Grade 5 Events**

7.3.4 Protocol-Specific Adverse Event Reporting Exclusions

Only events that are considered possibly, probably or definitely related to the study drug will be captured on the database for the purpose of this study.

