5.1 Unblinding

In the event of a medical emergency where breaking the blind is required to provide medical care to the subject, the primary investigator or treating investigator with approval by the primary-investigator may obtain the treatment assignment directly from the research pharmacy. Blinding of study treatment is critical to the integrity of this clinical trial and therefore, if a subject's treatment assignment is disclosed to the investigator, the subject will have study treatment discontinued. Documentation of the decision to unblind will be recorded in the subject's medical record.

After primary outcome measures are collected (blood collection at 6 month end of treatment visit), participants will have the option to learn their treatment assignment (be unblinded) and any patients randomized to the metformin arm will be invited to continue to take metformin for an additional 6 months on a crossover arm. Participants randomized to the placebo will discontinue study medication at the 6-month time point.

In addition, at the end of the study the PI will obtain a list from the research pharmacy of each patient's randomization for data analysis.

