7.6 Routine Adverse Event Reporting

Any Adverse Events related to metformin administration that led to dose-reductions or discontinuation of study medication **must** be reported in routine study data submissions to the PI on the toxicity case report forms. **AEs reported through expedited processes (e.g., reported to the IRB, FDA, etc.) must also be reported in routine study data submissions.**

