8.1.8 Blinding and Unblinding Methods

In the event of a serious adverse event or other circumstance requiring unblinding, the investigator will contact the research pharmacy, who will then unblind the subject to the investigator if necessary. If the treatment blind is broken, the reason and the date should be

recorded and signed by the investigator. Participants will have the option to be unblinded after the primary outcome measures have been collected.

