10. STUDY CALENDAR

Registration and randomization should be conducted within 28 days (4 weeks) of baseline assessments. The 3-month safety labs should ideally be performed within 7 days of scheduled day 84 (preferably before). End of study/6- (or 12-) month assessment should ideally be completed within 7 days of last dose of study drug for those who completed 6 (or 12) months of treatment, or for those who were not able to complete 6 months of treatment, within 7 days of the 6 month timepoint or as close as feasible. Assessments must be performed prior to administration of any study agent and only after signing consent unless done as part of standard of care procedure. Each cycle is defined as 28 days.

	Screening/ Baseline	Day 1	Day 7	End of Cycle 1 (Day 28)	Day 48 (Optional)	End of Cycle 3 (Day 84)	End of Cycle 6 (Day 168)	End of Study Visit ¹⁰	Survival Follow Up ¹¹	EDC Timepoints
Metformin/Placebo ¹		-----Day 1-168-----								Day 1-168
Informed consent	X									N/A
Telephone Drug Adherence /AE Collection ²			X	X	(X)	X		X		N/A
Questionnaire/Survey ³	X							X		Baseline and EOT
Demographics	X									Baseline
Serum or Urine Pregnancy Test (if applicable)	X									Baseline
Medical history	X									Baseline
Physical exam ⁴	X				(X)			X		Baseline and EOT
Vital signs (BP, respiratory rate, temperature)	X							X		Baseline and EOT
Height	X									Baseline
Weight	X							X		Baseline and EOT
Performance status	X							X		Baseline and EOT
CBC w/diff, plts ⁵	X				X			X		Baseline and EOT
Serum chemistry ⁶	X				X			X		Baseline and EOT
Serum Free Light Chains (SFLC) Serum Protein Electrophoresis (SPEP), Immunofixation (SIFX), and Quantitative Immunoglobulins	X							X		Baseline and EOT
Research Bone Marrow Aspirate and Core ⁷	X							X		If a bone marrow biopsy or aspirate is performed at any time during the study as part of SOC, it should be captured in Inform
Research Blood Collection ⁸	X							X		N/A
Adverse Event Collection ⁹		From Time of Informed Consent to 30 days from Last Dose of Metformin								Record related AEs in database only

Survival and Event Collection ¹¹				X	N/A
1 Enough drug will be supplied for 3 cycles at a time. Labs will be reviewed prior to shipment of any medication. Participants may be shipped drug directly to their home following local policy, and will be instructed to return any unused drug, empty bottles, and completed diaries in pre-labeled return packaging to the lead site if they do not present in person to clinic.					

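### Optional unblinding can come before the 6-month questionnaire, and related-only adverse event entry conflicts with the rule for expedited events

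*Combined protocol and SAP*

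**What the plan says.** **Unblinding.** Section 5.1 sets the point of release: "After primary outcome measures are collected (blood collection at 6 month end of treatment visit), participants will have the option to learn" their assignment. Section 8.1.8 is less specific: "Participants will have the option to be unblinded after the primary outcome measures have been collected". Sections 1.1, 3.1.7, 4.2, 5, 5.8 and 9.4.11 give the same option and tie it to the primary endpoint, outcome or assessments. Section 9.3 defines the primary endpoints as M-protein and light chains. Section 9.2 lists the Final Questionnaire among what is done at the end-of-study visit, which it introduces as the visit for the primary outcome assessments. Footnote 3 of the study calendar allows questionnaires to be returned in person, by mail, through RedCap or in another acceptable way. Change in quality of life to 6 months is a secondary objective in section 1.3; section 2.5.3 calls it exploratory.

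**Adverse events.** Section 7.3.4 restricts entry: "Only events that are considered possibly, probably or definitely related to the study drug will be captured on the database". Both calendars repeat this in the data-capture column: "Record related AEs in database only". Section 7.3.3 lists what must be reported to the sponsor-investigator. It includes "ALL CTCAE Grade 5 Events" and, for grade 4, the instruction "Report all events that are Unexpected". Neither carries a condition on attribution. Section 7.6 then states: "AEs reported through expedited processes (e.g., reported to the IRB, FDA, etc.) must also be reported in routine study data submissions". Separately, section 7.3.2 has investigators report any adverse event to the principal investigator, up to 30 days after the last dose, and section 11.2 names all adverse events as material the DSMB may receive.

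**The concern.** Quality of life is self-reported, and section 2.5.3 bases the objective on anxiety, distress and the psychosocial benefit of being offered a treatment. Such an outcome can shift when a participant learns the arm, the more so because those on placebo then stop study medication while those on metformin may continue. If the assignment can be released after the blood draw but before the questionnaire is returned, part of the 6-month comparison is no longer blind.

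For adverse events there are two difficulties. The database rule and the rule for expedited events give different instructions for a serious event judged not to be related. And a database filtered on attribution cannot show all-cause events by randomised arm, which is the safety description that a placebo group allows without any judgement of cause.

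**Working it through.** The plan states no figure on either matter, so the check is mainly a comparison of texts.

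**1. Can the questionnaire follow unblinding?**
- Section 5.1 names one act that opens the option: the 6-month blood collection.
- Section 9.2 puts the questionnaire at the same visit, but only as something participants are asked to complete.
- Calendar footnote 3 permits return by mail or RedCap.
- No section makes release of the assignment depend on the questionnaire.

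A participant could give blood, learn the arm and answer later without any rule being broken.

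**2. Do the other sections close the gap?** Partly. Sections 1.1, 5.8 and 9.4.11 wait for completion of the outcome assessments. Section 9.2 uses similar wording for the visit that includes the questionnaire, so these three can be read as covering it. Sections 3.1.7, 4.2 and 5 refer to the primary endpoint or endpoints, and 8.1.8 to the primary outcome measures. The parenthesis in 5.1 is the only place that spells out what is meant, and it names blood alone.

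**3. Scale for quality of life, on assumptions only.** The documents give neither the share of late questionnaires nor the take-up of unblinding. Suppose 5% to 30% of questionnaires in each arm followed unblinding, and knowing the arm moved the metformin-placebo contrast among those by 0.2 to 0.5 SD.
- Bias = share × shift: 0.05 × 0.2 = 0.01 SD to 0.30 × 0.5 = 0.15 SD.
- Standard error with 30 per arm and no baseline adjustment: √(2/30) = 0.258 SD.
- Ratio: 0.01/0.258 = 0.04 to 0.15/0.258 = 0.58 of one standard error.

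Under these assumptions the effect is small unless many questionnaires are late.

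**4. Where do the adverse event rules collide?** For events judged unlikely or unrelated:

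| Event | 7.3.4 and calendars | 7.3.3 | 7.6, if reported by an expedited route |
|---|---|---|---|
| Grade 5 | not entered | reportable | must be in routine study data |
| Grade 4, unexpected | not entered | reportable | must be in routine study data |
| Grade 4, expected | not entered | need not go to the IRB | not triggered by 7.3.3 |
| Grade 2 or 3 | not entered | not reportable (a reasonable possibility of relation is required) | not triggered by 7.3.3 |

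The conflict lies in the first two rows.

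**5. All-cause table by arm.** The database holds related events only, so it cannot yield such a table. The documents give no event rates. As an illustration on assumptions, take 30 per arm, 30% to 70% of participants with an event, one event each, and 20% to 80% of events judged related. The number per arm absent from the database is 30 × rate × (1 − share related): from 30 × 0.3 × 0.2 = 1.8 to 30 × 0.7 × 0.8 = 16.8 participants.

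**The case against.** **On unblinding.** The questionnaire belongs to the same visit, and three sections can fairly be read as requiring that visit's assessments to be finished first. A reader might infer that the plan consistently permits unblinding before the questionnaire; the documents do not support that. What remains is the narrow wording of 5.1 together with remote return. A reader might also infer that answers given with the arm known would bias the mixed model in section 12.7. That section describes the secondary endpoint as biomarkers and does not mention quality of life, so its use for the questionnaire is an inference.

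**On the conflict.** Section 7.6 describes routine submissions as going to the principal investigator on toxicity forms, while 7.3.4 concerns the database, so they might be two channels. Section 7.3.3 is also not itself headed as expedited reporting. But no section states that the channels are separate, section 11.1.2 sends data forms to the data office, and section 7.2 refers to the section after it as the one on expedited reporting. The objection shows that the conflict is narrow, not that it is absent. Deaths are also caught in part as a reason for leaving the study (5.9) and in survival follow-up (5.8).

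**On the all-cause table.** A reader might infer that all-cause information is not collected, or that the filter favours one arm. Neither holds. Section 7.3.2 sends any event to the principal investigator, and section 11.2 lets all events go to the DSMB. During the 6 months attribution is made blind, so information is lost in both arms. No between-arm comparison of adverse events is planned, and the stopping rules in 12.9 use related events. Related-only entry for a marketed drug in 60 participants is a defensible use of resources, so the extra table is optional.

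**Conclusion.** The point holds as an inexpensive improvement of low to modest severity. The M-protein endpoint is a laboratory value taken before the optional unblinding and is unaffected.

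- Section 5.1, read with the calendar footnote, leaves room for some 6-month quality-of-life answers to be given with the arm known. How many, and with what effect, cannot be estimated from the documents; the 0.01 to 0.15 SD range shown is assumption.
- Sections 7.3.4 and both calendars conflict with 7.3.3 and 7.6 for grade 5 and unexpected grade 4 events that are judged unlikely or unrelated and reported by an expedited route. This rests on treating the 7.3.3 list as expedited reporting and routine study data as including the database. The texts must be reconciled.
- An all-cause table by arm cannot be produced from the study database. It might still be rebuilt by hand from the forms sent to the principal investigator.

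**What to change.** **Unblinding.** In 5.1 and 8.1.8, release the assignment for optional unblinding only after the 6-month blood draw and the Final Questionnaire (or a documented refusal), with adverse event attributions to date entered. Emergency unblinding is unchanged. The cost is a short delay in unblinding, or in supply for the extension, if the questionnaire is late; completing it at the visit avoids this.

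**Adverse events.** Reconcile 7.3.4 and both calendars with 7.3.3 and 7.6 by entering the events already reported to the principal investigator, with grade and attribution as fields. The cost is more data entry for 60 participants. Adverse events are already asked about at scheduled contacts, so no new contact is needed.

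**Optional.** A descriptive table of all-cause and related events by arm for the blinded 6 months then becomes possible. Events in the 30 days after the last dose may still be attributed with the arm known. They can be flagged by the unblinding date, since 8.1.8 already provides that "If the treatment blind is broken, the reason and the date should be" recorded, but the change does not remove that limitation.

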7.4 Reporting to the Food and Drug Administration

The Investigator will be responsible for all communications with the FDA. The Investigator will report to the FDA, regardless of the site of occurrence, any serious adverse event that meets the FDA's criteria for expedited reporting following the reporting requirements and timelines set by the FDA.

